Comparison of LigaSure to Conventional Electrocoagulation in Video-assisted Thoracoscopic Surgery Lobectomy, NCT03125798 June 10, 2016

This study was powered for superiority in accordance with the data for total chest drainage volume in patients after VATS lobectomy and lymphadenectomy with monopolar electrocautery; these data were obtained from the institutional database (2013–2015; $n = 278$). If the mean total postoperative chest drainage volume were 750 ± 250 mL, and if the dropout rate were 10%, a sample of 214 patients (107 patients per group) would provide at least 85% power to detect a clinically important difference of 125 mL for this endpoint between the two groups, according to two-sided tests with a 5% level of significance.

The analyzed data were calculated as means \pm standard deviations, medians, minimum and maximum values, interquartile ranges (IQRs; quartile 1 to quartile 3), or percentages, as appropriate. We used the Shapiro–Wilk test to check normality of distribution and Levene’s test to check equality of variances. To compare the two unpaired groups, we used the unpaired t test for data that followed a normal distribution and had homogeneity of variances; otherwise, we used the Mann–Whitney U test. To analyze categorical data, we used the χ^2 test when the sample size was larger than 40 and all expected values were greater than 5; for other situations, we used Fisher’s exact test or the χ^2 test with Yates’s correction; or the Fisher-Freeman-Halton test for contingency table larger than 2×2 with any expected values was less or equal to 5. All results were considered significant when $p < 0.05$. To perform statistical analyses, we used Statistica 13.0 (StatSoft, Dell, Round Rock, TX, USA) or StatXact 11.0 (Cytel, Cambridge, MA, USA).

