Comparison of LigaSure to Conventional Electrocoagulation in Video-assisted

Thoracoscopic Surgery Lobectomy

NCT03125798

June 10,2016

Aim: to compare the short-term results of and extent of surgical injury by the LigaSure device and monopolar electrocautery in patients undergoing VATS lobectomy with lymphadenectomy.

Type of study: Pragmatic, parallel group, randomized controlled trial, simple randomization, 1:1 allocation ratio

Approval: Bioethics Committee of the Poznan University of Medical Sciences, Poznan, Poland

Location: Department of Thoracic Surgery, Poznan University of Medical Sciences

Inclusion criteria: admission for VATS lobectomy and lymphadenectomy for suspected or confirmed primary lung cancer, age of 18 years or older, ability to read and understand the information regarding the study, and ability to give informed consent to participate.

Exclusion criteria: preoperative radiotherapy or chemotherapy, prior mediastinoscopy or other surgical procedures involving the mediastinum, and ipsilateral chest surgery. Patients who underwent conversion from VATS to thoracotomy were assessed for the relationship between conversion and intervention, but their data were excluded from the final analysis to avoid confounding.

Enrollment: by the thoracic surgeons at admission to the department

Interventions: tissue dissection with the LigaSure device (the study group) or dissection with monopolar device (the control group).

Concealment: to conceal assignments, sequentially numbered, opaque, sealed envelopes that will be prepared before the study and will be opened just before the surgery. From this point, patients' assignments will be known to the surgeons.

Surgery: after induction of general anesthesia, a temperature probe will be inserted into the patient's esophagus and positioned at the level of subcarinal nodes. VATS lobectomy and lymphadenectomy will be performed with either the monopolar device or the LigaSure device. At the end of the surgery, one 24-F chest tube will be inserted into the pleural cavity and connected to a digital drainage system. The chest tube will be removed after resolution of air leak and when the fluid volume was <250 mL for 24 h.

The primary outcome measure: postoperative drainage volume

Secondary outcome measures: change in the esophageal temperature at the level of the subcarinal lymph nodes during lymphadenectomy and C-reactive protein levels 72 h after surgery.

Data collection:

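### Does the SAP's 214 patients for at least 85% power, where its inputs need 164, show that a stated input is wrong?

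*SAP*

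**What the plan says.** The opening paragraph of the SAP gives the whole sample size statement. The planning values are in "If the mean total postoperative chest drainage volume were 750 ± 250 mL", taken from the institution's own database of 278 patients treated in 2013–2015, with a 10% dropout allowance. The target is "a clinically important difference of 125 mL for this endpoint between the two groups", tested "according to two-sided tests with a 5% level of significance". The result is that "a sample of 214 patients (107 patients per group) would provide at least 85% power to detect a clinically important difference of 125 mL".

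The Protocol (type of study) adds "simple randomization, 1:1 allocation ratio". It names one primary outcome, postoperative drainage volume, and two secondary outcomes. Its exclusion criteria also remove patients converted to thoracotomy from the final analysis.

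The SAP's second paragraph compares the groups with the unpaired t test, or with the Mann–Whitney U test if normality or equal variances fail. The SAP does not name the sample size formula, and mentions no allowance for the rank test or for multiple endpoints.

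**The concern.** A sample size paragraph should let a reader get from the inputs to the number. Here every usual input is given, and the number that comes out is 164, not 214. A 30% excess is too large for rounding. It raises the suspicion that 107 per group came from something the SAP does not state, such as a larger standard deviation, a smaller target difference, heavier losses or a stricter significance level.

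If so, two things would be at stake. A hidden input such as a split significance level might belong in the analysis as well as in the planning. And a null result would be read against 85% power when the trial had more.

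**Working it through.** **Inputs.** Difference 125 mL, standard deviation 250 mL (reading the figure after ± as a standard deviation), two-sided 5%, power 85%, dropout 10% (all from the SAP); 1:1 allocation (Protocol). Standardised difference: 125/250 = 0.5.

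**Trying to reproduce 214.** The normal approximation per group is n = 2(z₀.₉₇₅ + z₀.₈₅)²/0.5² = 8 × (1.960 + 1.036)² = 71.8, so 72. With dropout, 72/0.9 = 80, or 160 in total. The noncentral t gives 72.8, so 73; then 73/0.9 = 81.1, so 82 per group and **164 in total**. The excess is 214 − 164 = 50, and 50/164 = 30%.

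**Other routes at the stated inputs and 85% power**

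| Variant | Total with 10% dropout |
|---|---|
| One-sided test | 130 to 132 |
| Mann–Whitney, efficiency 0.955 | 172 |
| Mann–Whitney, 15% inflation | 188 |
| Mann–Whitney, worst-case efficiency 0.864 | 190 |

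None reaches 214. Higher power with the t test does not give it either: 192 for 90% and 234 for 95%.

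**What 214 delivers.** 107 × 0.9 = 96.3, so about 96 evaluable per group.

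| Test at 96 per group | Power for 125 mL |
|---|---|
| t test | 93.1% |
| Mann–Whitney, efficiency 0.955 | 92.0% |
| Mann–Whitney, efficiency 0.864 | 89.3% |

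All three exceed 85%. With no dropout, 107 per group gives 95.4% (t test).

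**How far the margin stretches.** By the t test, 96 per group still gives 85% power if the standard deviation is 288 mL instead of 250, or if the difference is 109 mL instead of 125. Losses could reach 1 − 73/107 = 32% before the t test fell to 85%.

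**Can the hidden input be identified?** Three settings give 107 per group with the t test:

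- alpha 0.05/3 with 85% power: 95.6, so 96; 96/0.9 = 106.7, so 107
- alpha 0.01 with 80% power: 95.1, so 96; again 107 after dropout
- alpha 0.01 with 85% power and no dropout allowance: 106.1, so 107

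By the normal formula, the first gives 94.1, so 95, then 106 per group and 212 in total. Several exact matches from different settings identify none of them.

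**The case for a change.** The strongest case for a change is that the sentence exists to show where 214 comes from, and it fails to. Someone obtained 107 by a particular calculation, and the printed inputs are not that calculation. A three-way split of the 5% level matches exactly, and the Protocol lists exactly three outcomes. If that was the plan, testing everything at 0.05 would conflict with the design. The 10% may also leave out patients converted to thoracotomy, who are removed from the analysis. One added sentence would settle all this at no cost in patients, and it would tell readers that the type II error at 125 mL is about 7% and not 15%.

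The arithmetic in this case stands, and so does the remark that 214 is unexplained. The inference does not. The three-way split is one of several matches, and it contradicts the SAP's stated 5% level and the Protocol's single primary outcome. A larger allowance for conversions is possible, but it would be a reason for the margin, not a fault: the size tolerates losses of up to 32%. The case also passes over the simplest reading, a deliberate margin with every stated input correct. As for a null result, "would provide at least 85% power to detect a clinically important difference of 125 mL" understates its strength, which is the cautious direction. Such a result is in any case judged on the observed difference and its precision. With a standard deviation of 250 mL and 96 per group, the standard error is 250 × √(2/96) = 36.1 mL and the 95% half-width is 1.96 × 36.1 = 70.7 mL, whatever power was quoted.

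**Conclusion.** No change to the plan is needed. The stated inputs call for 164 patients, and 214 is 50 more for a reason the documents do not give. But the SAP states a minimum power, and the design exceeds it under both planned tests: 93.1% with the t test, and 89.3% to 92.0% with Mann–Whitney. A trial run exactly as written delivers what it promises, and no estimate, test or conclusion depends on how 214 was reached. Carrying a guessed significance level into the analysis would replace a clear stated rule with speculation.

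This rests on three assumptions: the ± figure is a standard deviation, losses are near 10%, and the standard deviation is near 250 mL in both groups. The conclusion has room on the last two, since t-test power stays at or above 85% for losses up to about 32% at 250 mL, or for a standard deviation up to about 288 mL at 10% loss. Simple randomisation may leave the groups somewhat unequal, which costs little: a split of 84 and 108 evaluable patients still gives 92.8% with the t test. A report of the trial could usefully mention the power of about 93%, but that is a matter of presentation.

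### Normal data with unequal variances are sent to Mann–Whitney, which does not hold the 5% level when centres are equal and spreads differ; Welch's t test would

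*SAP*

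**What the plan says.** The second paragraph of the SAP sets one rule for every continuous comparison of the two groups. Normality is checked with Shapiro–Wilk, and the SAP uses "Levene’s test to check equality of variances". The unpaired t test applies only to data that pass both checks, that is, data that followed a normal distribution and "had homogeneity of variances; otherwise, we used the Mann–Whitney U test". No unequal-variance t test is named.

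The sample-size paragraph sets the error rate, "according to two-sided tests with a 5% level of significance", and the methods paragraph applies the same 0.05 threshold throughout ("All results were considered significant when"). The trial is powered on a difference in means, "a clinically important difference of 125 mL", with one SD for both arms: "mean total postoperative chest drainage volume were 750 ± 250 mL". Neither document gives an SD for each arm, for this or any other outcome.

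The Protocol (Type of study) specifies simple randomization at 1:1. Under Exclusion criteria it removes converted patients from the final analysis. Both can leave the analysed arms unequal in size.

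**The concern.** Mann–Whitney takes its standard error from the hypothesis that the two distributions are identical, and the exact form of the test rests on the same hypothesis. A Levene rejection is evidence against that hypothesis. The rule therefore picks this test in the situation where its variance formula is least supported.

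At stake is the false-positive rate for an outcome with the same centre but different spread in the two arms. Any continuous outcome can enter the branch. One candidate is the secondary outcome "change in the esophageal temperature at the level of the subcarinal lymph nodes during lymphadenectomy", if one device heats tissue in some patients and not in others, though the documents contain no temperature data.

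There is also a loss of scale. Mann–Whitney gives no comparison of means, which is what the sample size was built on. For strictly normal data, equal means and P(X<Y) = 1/2 are the same condition, so the direction of the comparison survives. The calibrated test of a mean difference does not.

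**Working it through.** **Plan's own figure.** Inputs from the SAP: difference 125 mL, SD 250 mL, two-sided 5%, power 85%, dropout 10%.

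- n per arm = 2 × (1.960 + 1.036)² × (250/125)² = 71.8, so 72 (73 by the t distribution).
- After dropout: 72/0.9 = 80 per arm, 160 in total. The SAP states 107 and 214, which this does not reproduce.
- Analysed at the stated size: 107 × 0.9 = 96 per arm, with power about 93%. The claim of "at least 85% power to detect a clinically important difference of 125 mL" is true as a lower bound. The mismatch does not bear on this point. What follows uses 96 per arm, 192 in total.

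**Error rate of the branch.** Assume normal data, equal means and SD ratio r. Let n1 be the size of the arm with the smaller SD and n2 that of the arm with the larger SD.

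- Variance the test assumes for its estimate of P(X<Y): V0 = (n1 + n2 + 1)/(12·n1·n2).
- True variance: V = [(n2 − 1)·a + (n1 − 1)·b + 1/4]/(n1·n2), with a = arcsin(1/(1 + r²))/(2π) and b = arcsin(r²/(1 + r²))/(2π).
- Large-sample size = 2 × [1 − Φ(1.960 × √(V0/V))].

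At r = 1, a = b = 1/12, V = V0 and the size is 5.0%, as it should be.

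Example, r = 2, 96/96: a = 0.0320 and b = 0.1476. The numerator of V is 95 × 0.1796 + 0.25 = 17.32, against 193/12 = 16.08 assumed. The ratio is 1.077, the effective critical value is 1.960/√1.077 = 1.889, and the size is 5.9%.

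Example, r = 2, larger SD in the smaller arm (n1 = 106, n2 = 86): 85 × 0.0320 + 105 × 0.1476 + 0.25 = 18.47. The ratio is 1.148 and the size is 6.7%.

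| SD ratio (assumed) | 96/96 | 86/106, larger SD in smaller arm | 86/106, larger SD in larger arm |
|---|---|---|---|
| 1.25 | 5.1% | 5.4% | 4.8% |
| 1.5 | 5.3% | 5.8% | 4.8% |
| 2 | 5.9% | 6.7% | 5.1% |
| 3 | 6.9% | 8.1% | 5.7% |
| 4 | 7.6% | 9.0% | 6.3% |

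A simulation of 40,000 trials per cell, with the continuity-corrected test, agrees with every entry to within 0.2 points.

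**How often the branch is entered.** In simulation Levene rejects in a little over half of trials at ratio 1.25, in 95% at 1.5 and in essentially all at 2 or more.

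**Comparators.** Welch's test stays at about 5% (4.9% to 5.2%) in the unequal-variance cells of the same simulation. The pooled t test also stays near 5% in equal arms at these ratios. It fails only when arms are unequal: at ratio 2 it is about 6.7% with the larger SD in the smaller arm and about 3.5% in the reverse case.

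**How likely the imbalance is.** With 192 patients under simple randomization, a split of 86/106 or worse has probability about 17%. The chance that one specified arm has 86 or fewer is about 8.5%. The 95% range for an arm is 82 to 110. At 82/110 and ratio 2, with the larger SD in the smaller arm, the size is 7.1%.

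**The case against.** The strongest reply is that the inflation is small and rests on conditions the documents do not establish.

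- **Size.** In equal arms at ratios up to 2 the excess is under one percentage point. This stands.
- **Ratios.** For drainage volume a ratio of 3 would put one SD at 3 × 250 = 750 mL around a mean of 750 mL, which is not credible for a normal, non-negative volume, or at 250/3 = 83 mL. This stands for the primary outcome. For temperature change the ratio is simply unknown.
- **Which null.** If the devices do not differ at all, both arms share one distribution, Levene rejects only by chance, and Mann–Whitney within the branch stays near 5%. Inflation needs equal centres with different spread. A device that heats tissue in some patients would usually move the mean as well, and a rejection would then not be a false positive. This stands, and it limits how far the temperature example can be pressed.

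A reader might infer that the branch runs at 6% to 9% as a rule. The table does not support that: in equal arms 6% needs a ratio above 2, and 9% needs a ratio of 4 together with the larger SD in the smaller arm of an 86/106 split. A reader might also infer that unequal variances damage the pooled t test just as much. In the equal arms the trial plans, they do not.

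None of this defends the choice of Mann–Whitney for normal data with unequal variances. In equal arms the switch replaces a test that holds 5% with one that does not. In unequal arms Welch holds 5% and neither of the SAP's two tests does so reliably.

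**Conclusion.** The point holds in a limited form. For normal outcomes with equal centres and different spread, the rule leads to a test that does not hold the stated level. With 192 evaluable patients:

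- SD ratios up to 2: about 5% to 6% in equal arms, and 4.8% to 6.7% at an 86/106 split.
- SD ratios of 3 to 4: about 7% to 7.6% in equal arms, and 8% to 9% with unfavourable imbalance. If the larger SD is in the larger arm, only about 6%.

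These figures assume normality, exactly equal means and SD ratios that the documents do not supply. The documents do not show that the primary comparison has an inflated error rate, nor do they say that the switch was meant to protect the 5% level. The calculation covers normal data only, so it says nothing for or against Mann–Whitney where normality fails.

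**What to change.** Delete the Levene step. Compare the two groups with Welch's unequal-variance t test wherever the data are treated as normal, whatever the variances look like. This also keeps those outcomes on the mean-difference scale of the sample-size calculation.

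The cost is one sentence of SAP text. With equal variances and about 96 per arm the power loss against the pooled t test is negligible. Where variances differ, Welch gains about 2 points of power over Mann–Whitney in simulation. Replacing Mann–Whitney for non-normal data, for example with Brunner–Munzel, is a separate choice that this check does not test, and it is not part of the change proposed here.

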1. Preoperative data: baseline characteristics, comorbidities, results of pulmonary function tests, laboratory tests results, and results of preoperative risk assessment.
2. Surgery data: approach, type of lobectomy, numbers of lymph nodes and lymph node stations removed, duration of surgery, and estimated blood loss, esophageal temperature

3. Postoperative data: ICU admission, 24-hour and 48-hour and total volume of chest tube drainage, chest tube duration, laboratory evaluation of the pleural fluid composition after 24-hours (WBC, triglycerides, albumin), hospital stay, complications

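### The SAP lets all 16 non-primary comparisons be called significant at p<0.05 on the same rule as the primary, with no testing order, adjustment or exploratory label

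*SAP*

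**What the plan says.** The SAP's analysis paragraph states one significance rule: "All results were considered significant when" p is below 0.05. Neither document gives a testing order, a multiplicity adjustment or an exploratory label.

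The Protocol names one primary outcome, postoperative drainage volume, without a time window. The SAP sizes the trial on total volume. Two outcomes are ranked below it ("Secondary outcome measures: change in the esophageal temperature" and CRP at 72 h). The Protocol's data-collection list then adds many variables recorded during and after surgery, for example "ICU admission, 24-hour and 48-hour and total volume of chest tube drainage". The exclusion criteria add that conversion is examined against the intervention.

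The SAP's sample-size paragraph concerns the single endpoint. It says that 214 patients "would provide at least 85% power to detect a clinically important difference of 125 mL", "according to two-sided tests with a 5% level of significance".

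**The concern.** The SAP is not merely silent on multiplicity. It gives a rule under which any comparison with p<0.05 counts as a significant result. The primary and secondary labels in the Protocol do not limit that rule.

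The risk is concrete here because several of the other variables are close to the primary. The 24 h and 48 h volumes are parts of the total volume, and chest tube duration depends on fluid volume through the Protocol's removal criterion. The Protocol also leaves the time window of the primary open. If total volume shows no difference, a chance p<0.05 at 24 h or 48 h could be presented as support for the device, and the SAP's rule would allow it.

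**Working it through.** **Counting the comparisons**

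- Named secondaries: temperature change and 72 h CRP, 2.
- Surgery data: nodes, stations, duration, blood loss, 4. Approach and type of lobectomy are left out as descriptors.
- Postoperative data: ICU admission, 24 h volume, 48 h volume, tube duration, pleural WBC, triglycerides, albumin, stay, complications, 9. Total volume is the primary and is not counted.
- Conversion, 1.

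The further variables number 4 + 9 + 1 = 14, and all non-primary comparisons number 2 + 14 = 16.

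**Chance of at least one false claim if the devices do not differ**

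For k independent tests at 5% the chance is 1 − 0.95^k.

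- Two secondaries: 1 − 0.95² = 9.8%.
- All 16: 1 − 0.95^16 = 56.0%. Without conversion, 1 − 0.95^15 = 53.7%.
- Expected number of false results among 16: 16 × 0.05 = 0.8, whatever the correlation.

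The documents give no correlations, so a common correlation between the 16 test statistics is assumed and varied:

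| Assumed correlation | Chance of at least one false claim among 16 |
|---|---|
| 0 | 56% |
| 0.2 | 52% |
| 0.3 | about 48% |
| 0.5 | about 37% |

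Three of the 16 (ICU admission, conversion, complications) are categorical. If they are rare, the SAP's rule can lead to Fisher's exact test, which is conservative. At assumed event rates of 2% to 5% with 96 per group, its true size is about 0.4% to 2.0%. Leaving these three out altogether gives 1 − 0.95^13 = 49% if independent, and 45% to 33% at correlations of 0.2 to 0.5.

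**The power sentence**

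Inputs from the SAP: difference 125 mL, SD 250 mL (d = 125/250 = 0.5), two-sided 5%, 85% power, 10% dropout, 1:1 allocation.

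- Normal approximation: n = 2(1.960 + 1.036)²/0.5² = 71.8, so 72 per group. The exact t calculation gives 73.
- With dropout: 73/0.9 = 81.1, so 82 per group and 164 in total. The stated figure is 107 per group and 214 in total, so it is not reproduced at 85% power.
- Power at the stated size: 107 × 0.9 = 96 evaluable per group, which gives 93.1% by the t test at two-sided 5%.
- The SAP switches to Mann–Whitney if normality or equal variances fail. With an assumed relative efficiency of 0.955 (normal data) or 0.864 (worst case), power with 96 per group is about 92% or 89%.

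The SAP's claim of at least 85% is therefore true, but loose.

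**The case against.** The strongest reply is that one pre-specified primary needs no adjustment, and that statisticians differ on whether secondaries in a single-centre pragmatic surgical trial need formal gatekeeping. The first part stands in full. The second is fair as a general remark, but it argues for leaving secondaries unadjusted and labelled as supportive. It does not argue for a sentence that calls every result significant on one threshold.

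It can also be said that 13 of the 14 further variables come from a data-collection list, not an outcome list, and that neither document says a device claim will rest on them. That also stands, and it is why the count is given as approximate and the two named secondaries are reported separately. Misleading presentation after a null primary is a risk that the rule permits, not something the documents plan.

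A reader might infer that false claims are more likely than not. That holds only if the 16 outcomes are independent or weakly correlated. At a correlation of 0.3 the chance is already below 50%, and several of these outcomes are plainly related.

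**Conclusion.** The point holds as a gap in the rule for non-primary claims. If the devices do not differ, the SAP as written carries about a 10% chance of a false claim over the two named secondaries. Over all 16 non-primary comparisons the chance is roughly 37% to 56%. The range rests on an assumed common correlation of 0.5 to 0 and a full 5% error for each test, and it is somewhat lower if rare categorical outcomes go to Fisher's exact test. The primary inference is not affected.

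A reader might notice that 107 per group is what the t calculation gives at 0.05/3 = 0.0167 (96 evaluable, 96/0.9 = 106.7, power 85.2%), and infer that the sample size already pays for a correction over three outcomes. The documents do not support this:

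- The SAP sizes on one endpoint at 5% and mentions neither three outcomes nor 0.0167.
- The same 107 arises at alpha 0.01, with 80% power and 10% dropout, or with 85% power and no dropout allowance.
- The margin is thin. At 0.0167, power is 84.7% with 95 per group, and about 83% or 79% under Mann–Whitney at the two efficiencies above.
- No SD or target difference is given for temperature change or CRP, so their power cannot be computed.

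The case for the change does not need that argument, because the primary keeps its full 5%.

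**What to change.** Replace the significance sentence in the SAP with wording to this effect:

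- Total drainage volume is tested at two-sided 5%.
- Only if it is significant are temperature change and 72 h CRP tested, by Holm's procedure at an overall 5%: the smaller p-value against 0.025 and, if that passes, the other against 0.05.
- All other comparisons are reported as estimates with 95% confidence intervals, labelled exploratory and not called significant.

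Separately, restate the power sentence: 107 per group, 96 evaluable after 10% dropout, gives about 93% power at two-sided 5% under a t test, and about 89% to 92% under Mann–Whitney. At the stated inputs, 85% would need about 82 per group including dropout. An alpha of 0.0167 should not be written into the SAP. It is undocumented and would contradict testing the primary at 5%.

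The cost is a few sentences, with no extra data or patients and no loss of power for the primary. The downside is that a secondary claim then needs a significant primary result and a stricter first threshold (p<0.025).
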